Dose escalation and de-escalation in Phase 1 will follow the BOPIN design algorithm (Yuan and Liu 2016). Given the target DLT rate of 33% for INCB001158 in combination with daratumumab SC, the dose escalation and de-escalation rules are shown in Table 11. The BOPIN design also includes an elimination rule. When ≥ 3 participants have been treated, if the probability that the estimated toxicity rate that is above the target DLT rate is $> 95\%$ at a certain dose level, then this dose level and higher dose levels are assumed to be too toxic and will be eliminated. If the lowest dose level is eliminated, then the whole dose escalation will be terminated. Table 11 (in the bottom row) provides the elimination rules. Based on this algorithm, a minimum of 3 evaluable participants and a maximum of 9 evaluable participants will be enrolled at each tested dose level. The dose escalation will continue, based on the rules in Table 11, until at least 1 of the following occurs:

- Enrollment of additional participants at a dose level that already has 9 evaluable participants.
- Dose escalation to a dose level that has already been eliminated.
- Dose escalation above 100 mg BID.

At that point, the dose escalation will be stopped.

Table 11: Dose Escalation, De-Escalation, and Elimination Boundaries for Target DLT Rate of 33% in Phase 1

Action	Number of Evaluable Participants Treated at the Current Dose								
	1	2	3	4	5	6	7	8	9 ^a
Escalate if # of DLTs \leq	0	0	0	1	1	1	1	2	2
De-escalate if # of DLTs \geq	1	1	2	2	2	3	3	4	4
Elimination if # of DLTs \geq	N/A	N/A	3	3	4	4	5	5	6

DLT = dose-limiting toxicity; N/A = not applicable.

^a If 9 evaluable participants are enrolled at a dose level, and 3 of those participants experience a DLT, then the medical monitor and the investigators will review the entirety of the data and decide whether to escalate the dose level, de-escalate the dose level, or stop at that dose level.

The INCB001158 dose will be escalated using an open-label BOPIN design and a PAD or the MTD will be determined, or the maximum dose of INCB001158 (100 mg BID) will be reached.

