6.6.1. Definition of a Dose-Limiting Toxicity

A DLT will be defined as the occurrence of any of the toxicities in [Table 16](#) occurring from the start of study treatment up to and including Day 28, except those with a clear alternative explanation (eg, disease progression) or transient (≤ 72 hours) abnormal laboratory values

without associated clinically significant signs or symptoms based on investigator determination. All DLTs will be assessed for severity by the investigator using CTCAE v5 criteria. Participants who receive at least 42 of 56 ($\geq 75\%$) doses of study drug at the level assigned or have a DLT will be considered evaluable for determining tolerability of the dose. Participants who do not meet these criteria may be replaced to obtain sufficient evaluable participants to be able to assess that dose level using the BOIN design, as outlined in [Table 11](#).

Clear evidence of urea cycle inhibition (eg, an increase in fasting urinary orotic acid to $> 10 \times \text{ULN}$ or any orotic acid value of $> 40 \times \text{ULN}$, accompanied by plasma ammonia elevation $\geq 2 \times \text{ULN}$ and $\geq 2 \times \text{baseline}$, or symptomatic hyperammonemia) would be considered a dose-limiting event and will be treated the same as a DLT with regard to the dose-escalation rules and definition of the MTD described in Section [4.1.1](#). Refer to the INCB001158 [IB](#) for an explanation of the orotic acid thresholds.

Individual participant dose reductions may be made based on events observed at any time during treatment with study drug; however, for the purposes of dose level escalation/de-escalation, expanding a dose level, and for determining the MTD of INCB001158, decisions will be made based on events that are observed from the first day of study drug administration through and including the final day of Cycle 1 (Day 28). A lower MTD may subsequently be determined based on relevant toxicities that become evident after Day 28.

Table 16: Definition of a Dose-Limiting Toxicity

Toxicity	Definition

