Nonhematologic	
Any \geq Grade 3 nonhematologic toxicity EXCEPT the following:
Transient (≤ 72 hours) abnormal laboratory values without associated clinically significant signs or symptoms.Nausea, vomiting, and diarrhea adequately controlled with medical therapy within 72 hours.Fatigue or asthenia that was present at baseline or that lasts for < 7 days.An event clearly associated with the underlying disease, disease progression, a concomitant medication, or comorbidity.
Hematologic	
Grade 3 thrombocytopenia with clinically significant bleeding (requires hospitalization, transfusion of blood products, or other urgent medical intervention).Grade 4 hematologic toxicity, except for Grade 4 lymphopenia.Febrile neutropenia ($\text{ANC} < 1.0 \times 10^9/\text{L}$ and fever $> 101^\circ\text{F}/38.5^\circ\text{C}$).

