6.6.4. Procedures for Dose Level Review and Dose Escalation

Telephone conferences with study investigators will be scheduled by the sponsor in order to review dose level-specific data and overall safety data, to agree on dose escalation, to adjudicate individual high-grade AEs as potentially dose-limiting, and to guide other major study decisions.

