6.7.4. Dose Delays and Dose Modification of Daratumumab SC

Dose modification of daratumumab SC is not permitted. Dose delay is the primary method for managing toxicities related to daratumumab SC.

On the first day of each new treatment cycle and before each daratumumab SC administration, the participant will be evaluated by the treating physician for possible toxicities that may have occurred after the previous dose(s). Toxicities are to be assessed according to CTCAE v5. Dose delays will be made based on the toxicity experienced during the previous cycle of therapy or newly encountered on Day 1 of a cycle.

For all daratumumab SC doses in a treatment cycle except the first dose, if daratumumab SC administration does not commence within the prespecified window (see [Table 3](#) and [Table 4](#) for study site visit assessments prior to and post-crossover, respectively, and [Table 7](#) for all participants as of Protocol Amendment 3) of the scheduled administration date, then the dose will be considered a missed dose. Administration may resume at the next planned dosing date. A missed dose will not be made up. The minimal time interval between daratumumab SC doses should be 4 days.

Daratumumab SC treatment must be held if any of the following criteria below are met, to allow for recovery from toxicity, regardless of relationship to INCB001158 or daratumumab SC.

- Grade 4 hematologic toxicity, except for Grade 4 lymphopenia
- Grade 3 thrombocytopenia with bleeding
- Febrile neutropenia
- Neutropenia with infection, of any grade
- Grade 3 or higher nonhematologic toxicities, *with the following exceptions:*
 - Grade 3 nausea or Grade 3 vomiting that responds to antiemetic treatment within 7 days
 - Grade 3 diarrhea that responds to antidiarrheal treatment within 7 days

- Grade 3 fatigue that was present at baseline or that lasts for < 7 days after the last administration of daratumumab SC
- Grade 3 asthenia that was present at baseline or that lasts for < 7 days after the last administration of daratumumab SC.

Administration of daratumumab SC may be restarted (as indicated in [Table 18](#)) upon recovery from toxicity to Grade 2 or baseline, with the exception that Grade 2 laryngeal edema or Grade 2 bronchospasm must be fully recovered.

Table 18: Daratumumab SC-Related Toxicity Management

Cycles	Frequency	Dose Held	Dosing Re-Start at
1 and 2	QW	> 3 days	Next planned QW dosing date
3 to 6	Q2W	> 7 days	Next planned Q2W dosing date

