10.4.2.3. Vital Signs

Descriptive statistics and mean change from baseline will be determined for vital signs (blood pressure, pulse, respiratory rate, and body temperature) at each assessment time. Vital sign results will be reviewed for clinically notable abnormalities (see [Table 28](#)), and participants exhibiting clinically notable vital sign abnormalities will be listed. A value will be considered an "alert" value if it is outside the established range and shows a > 25% change from baseline.

Table 28: Criteria for Clinically Notable Vital Sign Abnormalities

Parameter	High Threshold	Low Threshold
Systolic blood pressure	> 155 mmHg	< 85 mmHg
Diastolic blood pressure	> 100 mmHg	< 40 mmHg
Pulse	> 100 beats/min	< 45 beats/min
Temperature	> 38°C	< 35.5°C
Respiratory rate	> 24 breaths/min	< 8 breaths/min

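### The febrile neutropenia DLT fever limit is printed as two different temperatures (101°F is 38.3°C; 38.5°C is 101.3°F), so events in a 0.17°C band are a DLT by one figure and not by the other

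*Protocol*

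**What the plan says.** Protocol Section 6.6.1, Table 16, has a hematologic row with three DLT items. One is febrile neutropenia, which needs ANC < 1.0 × 10^9/L together with "fever $> 101^\circ\text{F}/38.5^\circ\text{C", that is, a single limit written as 101°F/38.5°C. Another is "Grade 4 hematologic toxicity, except for Grade 4 lymphopenia", which carries no temperature condition.

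The classification is used in two ways:

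- **DLT count.** Table 11 in Section 4.1.1 turns the number of DLTs at a dose level into a decision (for example the row "De-escalate if # of DLTs").
- **Evaluability.** Under Section 6.6.1, participants who took at least 42 of 56 doses "or have a DLT will be considered evaluable for determining tolerability of the dose". For the rest, "Participants who do not meet these criteria may be replaced to obtain sufficient evaluable participants". SAP Section 5.3.3 uses the same definition.

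Other places that touch on the matter do not choose between the figures:

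- Section 6.7.4 lists "Febrile neutropenia" as a reason to hold daratumumab, with no temperature.
- Table 28, "Criteria for Clinically Notable Vital Sign Abnormalities", sets a 38°C limit, but for vital-sign listings.
- Section 6.6.4 provides calls "to adjudicate individual high-grade AEs as potentially dose-limiting", without a rule for this case.
- SAP Section 8.2.2 counts as a DLT whatever the Adverse Event eCRF records as one under the Protocol.

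**The concern.** A criterion stated in two units should give the same answer in either. This one does not, so two sites that both follow the text could classify the same patient differently, depending on the unit in which they read temperature.

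Dose levels were planned with 3 to 9 evaluable participants, so one event more or less can move a Table 11 decision. The MTD definition in Section 4.1.1 (fewer than 33% with a DLT) is equally sensitive. What remains at stake now is narrower: whether Phase 1 DLTs and membership of the DLT evaluable population are reported on one consistent definition (SAP Listings 2.7.2.1 and 2.3.1.x). The SAP drops the efficacy analyses and keeps safety, so these listings are part of what the study will still report.

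**Working it through.** **Inputs.** Fever and ANC limits: Table 16. Dose rule: Table 11, with target 33% and the 0.6 and 1.4 multipliers from Section 10.5.1. Evaluability: Section 6.6.1. Rounding practice: Table 14.

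**1. Do the two figures agree?**
- (101 − 32) × 5/9 = 38.33°C, not 38.5°C.
- 38.5 × 9/5 + 32 = 101.3°F, not 101°F.
- Difference: 38.5 − 38.33 = 0.17°C, or 101.3 − 101 = 0.3°F.

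If temperatures are recorded to 0.1 degree (an assumption), the readings in dispute are 38.4 and 38.5°C, or 101.1, 101.2 and 101.3°F.

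**2. Which events are affected?**
- Any reading above 38.5°C exceeds both limits.
- Grade 4 neutropenia is normally a DLT through its own item, whatever the temperature.
- What is left is neutropenia that is not Grade 4, with ANC < 1.0 × 10^9/L and a peak above 38.33°C and up to 38.5°C. The general exceptions in Section 6.6.1, such as a clear alternative explanation, still apply but do not select a temperature.

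**3. Does Table 11 work as printed?** With target 0.33 and limits 0.6 × 0.33 = 0.198 and 1.4 × 0.33 = 0.462, the BOIN cut-offs are 0.2604 (escalate) and 0.3947 (de-escalate). For n = 1 to 9 these give escalation at 0,0,0,1,1,1,1,2,2 or fewer DLTs and de-escalation at 1,1,2,2,2,3,3,4,4 or more. With a Beta(1,1) prior (assumed, since none is named), elimination for n = 3 to 9 is at 3,3,4,4,5,5,6. All three rows match Table 11, so the problem lies in the event definition and not in the boundaries.

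**4. What would one event in the band do?**

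*At least 42 doses taken.* Only the DLT count changes.

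| Evaluable n | One event as a share | Example under Table 11 |
|---|---|---|
| 3 | 1/3 = 33.3% | 0 DLTs: escalate; 1: stay |
| 6 | 1/6 = 16.7% | 1 DLT: escalate; 2: stay |
| 9 | 1/9 = 11.1% | 2 DLTs: escalate; 3: case review (table footnote) |

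*At most 41 doses taken* (41/56 = 73.2%, against the required 42/56 = 75.0%). The participant is evaluable only if the event is a DLT, so numerator and denominator both change. With no other DLT, the °C figure gives 0/3 and the °F figure 1/4 = 25.0%; likewise 0/8 against 1/9 = 11.1%. Table 11 says escalate in each of these four cases. With one other DLT, 1/3 (stay) becomes 2/4 (de-escalate).

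These are consequences given one such event. The documents give no rate for it, so no probability is attached.

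**5. Is there evidence of intent?** Table 14 prints the 2°C to 8°C storage range as 36°F to 46°F. Exactly, 2 × 9/5 + 32 = 35.6 and 8 × 9/5 + 32 = 46.4, so °F was rounded to whole degrees there. The same practice turns 38.5°C (101.3°F) into 101°F. The reverse does not work: 101°F rounded to one decimal is 38.3°C.

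**The case against.** The strongest reply is that this is rounding and not a conflict: 38.5°C is the limit, and 101°F is its whole-degree equivalent, as in Table 14. That is the better guess at intent, and it stands as such. But Table 14 concerns drug storage and states no rule for Table 16. A site reading in °F and following the text would still count 101.1 to 101.3°F as a DLT.

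A second reply also largely stands. SAP Section 8.2.2 takes DLTs from the eCRF, so no temperature rule is applied at analysis, and a new line in the SAP would not by itself alter Listing 2.7.2.1. The study was open-label, and sponsor and investigators reviewed high-grade events as they arose (Section 6.6.4), so a cut-off cannot now be fixed blind to the events.

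Third, the 38.5 appears only once, so the documents offer no cross-check against a misprint or misread digit. This is a reason to look at the source first.

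A reader might go further and infer that the recommended Phase 2 dose rests on a miscounted DLT. Nothing supports that: neither document reports any febrile neutropenia event, in or out of the band. A reader might also infer that 38.3°C should be adopted because it is the more inclusive. The documents give no ground for that preference, and what rounding evidence there is points to 38.5°C.

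**Conclusion.** The point holds, and it is minor. Table 16 prints one decision threshold as two temperatures 0.17°C (0.3°F) apart, and neither document says which governs. Only neutropenia that is not Grade 4, with ANC < 1.0 × 10^9/L and a peak above 38.33°C and up to 38.5°C, is classified differently. It is more than a typographical matter, because the threshold feeds the DLT count and DLT evaluability.

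The practical reach is small. Protocol Appendix F (Amendment 3) records that enrollment has ended, so escalation decisions are past. DLTs are listed and not tested, so no type I error, power or sample-size figure depends on this. What remains open is whether any recorded Phase 1 event lies in the band. The conclusion assumes that the printed digits are as in the source.

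**What to change.** 1. Confirm the 38.5 against the source document.
2. The sponsor states which limit was intended and prints one matched pair in Table 16: either > 38.5°C (101.3°F) or > 38.3°C (101°F). Both pairs are consistent. The first is exact. For the second, the lowest qualifying readings to 0.1 degree are 38.4°C (101.12°F) and 101.1°F (38.39°C), so the two units agree.
3. Check the recorded Phase 1 Cycle 1 events of neutropenia with fever that were not Grade 4 and had ANC < 1.0 × 10^9/L. Include events not recorded as DLTs and participants with fewer than 42 doses, since Listing 2.7.2.1 would not show them.
4. If a peak lies in the band, footnote Listing 2.7.2.1 with the classification used for the dose decision, and with the DLT status and evaluability under the other figure. If there is none, say so in one line.

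**Cost.** One line of text and a review of at most about 24 participants (up to 18 evaluable plus up to 6 backfill as planned, besides any replaced as not evaluable). Peak temperature is not among the adverse event attributes listed in Section 9.3, and vital signs are taken at visits, so an event near the limit may need a look at site source records.

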6.6.2. Management of Dose-Limiting Toxicities or Other Urgent Situations

Investigators may employ any measures or concomitant medications necessary to optimally treat the participant after discussion with the sponsor (whenever possible).

6.6.3. Follow-Up of Dose-Limiting Toxicities

Any DLT should be monitored until it resolves to baseline or appears to have stabilized for a minimum of 4 weeks, unless the participant discontinues study treatment, in which case, the participant will be followed for 28 days after last dose of study treatment or 90 days for irAEs (see Section [9](#)). During follow-up, participants should be seen as often as medically indicated to assure safety.

6.6.4. Procedures for Dose Level Review and Dose Escalation

Telephone conferences with study investigators will be scheduled by the sponsor in order to review dose level-specific data and overall safety data, to agree on dose escalation, to adjudicate individual high-grade AEs as potentially dose-limiting, and to guide other major study decisions.

6.7. Dose Modifications

Selections and modifications to the study treatment regimen are planned for dose-escalation. Dose interruptions and modifications also may occur for individual study participants. The identification of DLTs will define the doses used in planned dose levels (see Section 4.1.1). Further, the occurrence of DLTs and other toxicities (related or unrelated to study drug) will guide decisions for treatment interruptions and discontinuation for individual participants. Intraparticipant dose escalation for any study drug is not permitted.

6.7.1. Dose Modifications of INCB001158

For participants in Phase 1, dose reductions of INCB001158 will be permitted during the first 28 days only if a participant experiences a DLT or a toxicity that may herald a DLT. If a participant experiences a DLT, treatment continuation at a lower dose of INCB001158 will be permitted as long as the toxicity has returned to \leq Grade 1 or baseline within 28 days. When INCB001158 is held or discontinued, daratumumab SC may be continued, at the investigator's discretion. Upon recovery, participants may restart at 1 INCB001158 dose level lower. Participants who do not recover within 28 days will not be eligible for resumption of study treatment without approval from the medical monitor. See also [Table 17](#).

6.7.2. Criteria and Procedures for Dose Interruptions and Adjustments of Study Drug

Safety concerns should be discussed with the sponsor immediately upon occurrence or awareness to determine if the participant should continue or discontinue study treatment.

As described in Section 2.3, INCB001158 has the potential to cause toxicity related to the inhibition of arginase 1 in the hepatic urea cycle. [Table 17](#) provides guidance for INCB001158 dose modifications and participant management if there is evidence of urea cycle inhibition.

Dose modification and toxicity management for potential irAEs associated with INCB001158 should be managed as follows.

Adverse events (both nonserious and serious) associated with INCB001158 exposure may represent an immunologic etiology. These irAEs may occur shortly after the first dose or several months after the last dose of treatment and may affect more than 1 body system simultaneously. Therefore, early recognition and initiation of treatment is critical to reduce complications. For suspected irAEs, ensure adequate evaluation to confirm etiology or exclude other causes. Additional procedures or tests such as bronchoscopy, endoscopy, or skin biopsy may be included as part of the evaluation. Based on the severity of irAEs, withhold or permanently discontinue INCB001158 and administer corticosteroids.

[Table 17](#) summarizes the AE dose modification actions for INCB001158. Of note, when indicated by [Table 17](#) to mitigate irAEs, the dose of INCB001158 must be reduced using the dosing levels outlined in [Table 11](#). Once reduced, re-escalation of INCB001158 is not permitted.

Table 17: Guidelines for Interruption and Restarting of Study Drug

Adverse Event	Toxicity Grade or Conditions (CTCAE v5)	Action Taken	AE Management With Corticosteroid and/or Other Therapies	Monitor and Follow-Up
Evidence of urea cycle inhibition	
 Fasting urinary orotic acid $> 2 \times$ and $\leq 10 \times$ ULN Any urinary orotic acid $> 2 \times$ and $\leq 40 \times$ ULN 	
 Continue. 	
 None. 	
 Retest 1 week later. If still abnormal, withhold INCB001158 and retest every week until orotic acid returns to normal level, then consider restarting (at a lower dose) in consultation with medical monitor.
	
 Ammonia $2 \times$ ULN and $2 \times$ baseline (repeated measurements or with symptoms) Fasting urinary orotic acid $> 10 \times$ ULN Any urinary orotic acid $> 40 \times$ ULN BUN $< 50\%$ LLN 	
 Withhold. Consider restarting (at a lower dose) in consultation with medical monitor. 	
 See Section 6.7.3 for management of hyperammonemia. 	
Pneumonitis	Grade 2	
 Withhold until Grade 0-1. Restart at full dose. 	
 Administer corticosteroids (initial dose of 1-2 mg/kg/day prednisone or equivalent) followed by taper. 	
 Monitor participants for signs and symptoms of pneumonitis. Evaluate participants with suspected pneumonitis with radiographic imaging and initiate corticosteroid treatment. Add prophylactic antibiotics for opportunistic infections.
	Grade 3 or 4, or recurrent Grade 2	
 Withhold until Grade 0-1. Consider rechallenge at next dose level lower. 		

Table 17: Guidelines for Interruption and Restarting of Study Drug (Continued)

Adverse Event	Toxicity Grade or Conditions (CTCAE v5)	Action Taken	AE Management With Corticosteroid and/or Other Therapies	Monitor and Follow-Up
Diarrhea/colitis	Grade 2 or 3	
 Withhold until Grade 0-1. Grade 2: Restart at same dose level. Grade 3: Restart at next dose level lower. 	
 Administer corticosteroids (initial dose of 1-2 mg/kg/day prednisone or equivalent) followed by taper. 	
 Monitor participants for signs and symptoms of enterocolitis (ie, diarrhea, abdominal pain, blood or mucus in stool with or without fever) and of bowel perforation (ie, peritoneal signs and ileus). Participants with \geq Grade 2 diarrhea suspecting colitis should consider GI consultation and performing endoscopy to rule out colitis. Participants with diarrhea/colitis should be advised to drink liberal quantities of clear fluids. If sufficient oral fluid intake is not feasible, fluid and electrolytes should be substituted via IV infusion.
	Grade 4	
 Withhold until Grade 0-1. Consider rechallenge at next dose level lower. 		
AST/ALT elevation or increased bilirubin ^a	Grade 2	
 Withhold until Grade 0-1. Restart at same dose level. 	
 Administer corticosteroids (initial dose of 0.5-1 mg/kg prednisone or equivalent) followed by taper. 	
 Monitor with liver function tests (consider weekly or more frequently until liver enzyme value returns to baseline or is stable).
	Grade 3 or 4	
 Withhold until Grade 0-1. Consider rechallenge at next dose level lower. 	
 Administer corticosteroids (initial dose of 1-2 mg/kg prednisone or equivalent) followed by taper. 	
T1DM or hyperglycemia ^b	Newly onset T1DM or Grade 3 or 4 hyperglycemia associated with evidence of β -cell failure	
 Withhold until Grade 0-1. Grade 2: Restart at same dose level. Grade 3: Restart at next dose level lower. 	
 Initiate insulin replacement therapy for participants with T1DM. Administer antihyperglycemic in participants with hyperglycemia. 	
 Monitor participants for hyperglycemia or other signs and symptoms of diabetes.
Hypophysitis	Grade 2	
 Withhold until Grade 0-1. Restart at same dose level. 	
 Administer corticosteroids and initiate hormonal replacements as clinically indicated. 	
 Monitor for signs and symptoms of hypophysitis (including hypopituitarism and adrenal insufficiency).
	Grade 3 or 4	
 Withhold until Grade 0-1. Grade 3: Restart at same dose level. Grade 4: Consider rechallenge at next dose level lower. 		

Table 17: Guidelines for Interruption and Restarting of Study Drug (Continued)

Adverse Event	Toxicity Grade or Conditions (CTCAE v5)	Action Taken	AE Management With Corticosteroid and/or Other Therapies	Monitor and Follow-Up
Hyperthyroidism ^b	Grade 2	
 Continue. 	
 Treat with nonselective β-blockers (eg, propranolol) or thionamides as appropriate. 	
 Monitor for signs and symptoms of thyroid disorders.
	Grade 3 or 4	
 Withhold until Grade 0-1. Consider rechallenge at next dose level lower. 		
Hypothyroidism ^b	Grade 2-4	
 Continue. 	
 Initiate thyroid replacement hormones (eg, levothyroxine or liothyronine) per standard of care. 	
 Monitor for signs and symptoms of thyroid disorders.
Nephritis and renal dysfunction	Grade 2	
 Withhold until Grade 0-1. Restart at same dose level. 	
 Administer corticosteroids (prednisone 1-2 mg/kg or equivalent) followed by taper. 	
 Monitor changes of renal function.
	Grade 3 or 4	
 Withhold until Grade 0-1. Grade 3: Restart at same dose level. Grade 4: Consider rechallenge at next dose level lower. 		
Rash	Grade 1 or 2	
 Continue. 	
 Manage with topical steroids with or without drug interruption. 	
	Grade 3 ^c	
 Withhold until Grade 0-1. Restart at same dose level. 	
 Consider dermatology consultation and biopsy for confirmation of diagnosis. Administer corticosteroids (initial dose of 1-2 mg/kg prednisone or equivalent) followed by taper. 	
 If toxicity does not resolve within 12 weeks of last dose, or cannot taper below 10 mg or less of prednisone or equivalent within 12 weeks, must permanently discontinue.
	Grade 4	
 Withhold until Grade 0-1. Consider rechallenge at next dose level lower. 	
 Dermatology consultation and consideration of biopsy and clinical dermatology photograph. Administer corticosteroids (initial dose of 1-2 mg/kg prednisone or equivalent) followed by taper. 	

Table 17: Guidelines for Interruption and Restarting of Study Drug (Continued)

Adverse Event	Toxicity Grade or Conditions (CTCAE v5)	Action Taken	AE Management With Corticosteroid and/or Other Therapies	Monitor and Follow-Up
Asymptomatic ^d amylase or lipase increased	Grade 3	
 May continue treatment with medical monitor approval. 		
 Permanently discontinue if clinical signs and symptoms of pancreatitis develop (abdominal pain, nausea, vomiting). If toxicity does not resolve within 12 weeks of last dose after an interruption, must permanently discontinue unless approved by the medical monitor to continue. If Grade 4 lipase/amylase elevation is asymptomatic and abdominal imaging suggests no pathology, study drug administration dosing may continue with medical monitor approval.
	Grade 4	
 Withhold until Grade 0-1. Restart at same dose level. 		
All other irAEs	Grade 3, or intolerable/persistent Grade 2	
 Withhold until Grade 0-1. Consider rechallenge at next dose level lower. 	
 Based on severity of AE, administer corticosteroids. 	
 Ensure adequate evaluation to confirm etiology or exclude other causes
	Grade 4 or recurrent Grade 3	
 Withhold until Grade 0-1. Consider rechallenge at next dose level lower. 		

General Instructions:
 
 Corticosteroid taper should be initiated upon AE improving to Grade 1 or less and should be continued over at least 4 weeks. For situations where INCB001158 has been withheld, INCB001158 can be resumed after AE has been reduced to Grade 1 or 0 and corticosteroid has been tapered. INCB001158 should be permanently discontinued if AE does not resolve within 12 weeks of last dose or if corticosteroids cannot be reduced to ≤ 10 mg prednisone or equivalent per day within 12 weeks. For severe and life-threatening irAEs, IV corticosteroid should be initiated first followed by oral steroid. Other immunosuppressive treatment should be initiated if irAEs cannot be controlled by corticosteroids. 				

AE = adverse event; ALT (SGPT) = alanine aminotransferase (serum glutamic pyruvic transaminase); AST (SGOT) = aspartate aminotransferase (serum glutamic oxaloacetic transaminase); BUN = blood urea nitrogen; CTCAE = Common Terminology Criteria for Adverse Events; IV = intravenous; irAE = immune-related adverse events; LLN = lower limit of normal; T1DM = Type 1 diabetes mellitus; ULN = upper limit of normal.

^a Participants with radiographically documented liver metastases should withhold at $> 5 \times$ ULN.

^b For participants with Grade 3 or 4 immune-related endocrinopathy where withholding of INCB001158 is required, INCB001158 may be resumed when AE resolves to \leq Grade 2 and is controlled with hormonal replacement therapy or achieved metabolic control (in case of T1DM).

^c Participants with Grade 3 rash in the absence of desquamation, with no mucosal involvement, that does not require systemic steroids, and that resolves to Grade 1 within 14 days do not have to hold study medication and may be treated similar as Grade 1 events.

^d If Grade 4 lipase/amylase elevation is asymptomatic and abdominal imaging suggests no pathology, then study drug administration dosing may continue (with or without dose reduction) with medical monitor approval.

